**4.4 Time and Events Table**

	Baseline	
Screening	X	Within 2 weeks of baseline SOC imaging
Informed Consent	X	
SOC imaging	X	
Research Scan		X

**5.0 INVESTIGATIONAL DEVICE**

**5.1 Investigational Device Description**

We recently demonstrated a high-speed, and low-dose *stationary* digital tomosynthesis system (s-DCT) for 3D lung imaging[21]. The system is based on the carbon nanotube (CNT) x-ray source array technology invented by our team at UNC[22-24]. Instead of mechanically moving a large x-generator to different viewing angles for the projection images, s-DCT generates the images by electronically and sequentially activating the individual x-ray sources inside spatially distributed CNT x-ray source array without moving the source, detector or the patient. Our initial trial of lung nodule detection resulted in mixed results, with reasonable, but not sufficiently accurate identification of smaller lung nodules. One of the critical limitations is the reduction in image quality due to x-ray scatter, inherent in all x-ray based imaging systems.

As shown in Figure 1, the clinical test ready prototype device has already been constructed by retrofitting a commercial mobile digital radiography system with a dedicated CNT x-ray source array (XinRay Systems Inc., NC). A flat panel detector (Varian Inc., CA) is placed underneath the patient. An external collimator is connected to the source array to confine the x-ray radiation only to the region of interests to minimize the radiation to the patient and the staff.

[figure not shown]

Figure 1: A photograph of the stationary digital chest tomosynthesis imaging system with a CNT x-ray source array.

In all x-ray imaging approaches, the detector measures both the photons that have passed directly through an object (primary photons) and those that are scattered by the object (scattered photons). Unfortunately, only the primary photons are useful for imaging in conventional diagnostic imaging. The presence of scattered photons is a major source of image degradation and extra dose to the patient. Scatter also increases as the imaging subject thickness increases. The scatter-to-primary ratio (SPR) in mammography can vary from 30% to 150%. In chest radiography the SPR can vary from 100% to 500%. Conventional radiography systems use anti-scatter grids placed in front of the detector to block some of the scattered photons from reaching the detector. Unfortunately, the grids also block significant portion of primary beam, and thus a large increase in dose (up to 500%) is required to obtain the same exposure to the detector. Analytical approaches to reduce scatter, such as Monte Carlo simulations and using peripheral field for modeling are generally time consuming and inaccurate. The slot-scan method, though effective, is very slow and impractical for clinical applications.

We have extended our system by developing a scatter correction technique that can be applied to all of x-ray imaging, but is particularly useful in tomosynthesis scanning. Our approach is to estimate scatter by placing a large plate with holes that allow a small fraction (3%) of the primary beam to pass, which generates a patient specific scatter map. This scatter map can then be subtracted from the diagnostic scan.

Preliminary thoracic phantom and large animal imaging results have demonstrated the feasibility of our approach (Figure 2). Furthermore, by accurately estimating scatter, we

can also potentially reduce the dose of primary diagnostic scan. Our proposed implementation of the scatter reduction plate is in Figure 3.

[figure not shown]
[figure not shown]

Figure 2: Chest tomosynthesis image slice from a respiratory gated acquisition of a 30 kg normal pig model without (left) and with (right) scatter correction performed with the PSSC approach.

**Figure 1:** CAD drawing of the PSSC device designed to be implanted with s-DCT system which swings in front and away from the patient during the study. The PSSC can be rapidly moved in and out of the field to minimize the breath hold and patient imaging time.

The research images will not be interpreted or analyzed for clinical decisions related to the patient. As such, this study will request that the IRB make a determination that this study is no greater than minimal risk. This study meets all the requirements for an NSR determination including:

- The device will not be implanted.
- The device is not intended to support or sustain human life.
- The device is not being used of substantial importance in diagnosing, curing, mitigating, or treating disease.
- The device does not present a potential for serious risk to health, safety, or welfare of a subject.

## 5.2 Expected Risks

This research protocol presents minimal risk to participants, investigators and study personnel. The radiation dose from the device about 10% of the dose comparing to a low-dose CT. Hardware, though experimental, is built on an FDA approved system. The components that will physically have contact with the patient will be a part of the original

FDA approved device. Only the x-ray source has been modified. All x-ray and electrical interlocks will be maintained. Prior to implementation, this study will be reviewed by the Radiation Safety Committee.

## **6.0 UNANTICIPATED CONCERNS (DEVICES)**

### **6.1.1 Unanticipated Adverse Device Effect (UADE)**

The investigational device exemption (IDE) regulations define an unanticipated adverse device effect (UADE) as “any serious adverse effect on health or safety or any life-threatening problem or death caused by, or associated with, a device, if that effect, problem, or death was not previously identified in nature, severity, or degree of incidence in the investigational plan or application (including a supplementary plan or application), or any other unanticipated serious problem associated with a device that relates to the rights, safety, or welfare of subjects” (21 CFR 812.3(s)).

### **6.1.2 Unanticipated Problems (UP)**

As defined by UNC’s IRB, unanticipated problems involving risks to study subjects refers to any incident, experience, or outcome that:

- Is unexpected (in terms of nature, severity, or frequency) given (a) the research procedures that are described in the protocol-related documents, such as the IRB-approved research protocol and informed consent document; and (b) the characteristics of the subject population being studied;
- Is related or possibly related to a subject’s participation in the research; and
- Suggests that the research places subjects or others at a greater risk of harm (including physical, psychological, economic, or social harm) related to the research than was previously known or recognized.

### **6.1.3 Reporting**

#### **6.1.4 UADEs**

UADEs must be reported by the clinical investigator to the sponsor and the reviewing IRB, as described below:

For this device study, investigators are required to submit a report of a UADE to the FDA, the manufacturer of the device and the UNC IRB as soon as possible, but in no event later than 10 working days after the investigator first learns of the event (§ 812.150(a)(1)), using the MedWatch Form 3500A. Sponsors must immediately conduct an evaluation of a UADE and must report the results of the evaluation to FDA, the UNC IRB, and participating investigators within 10 working days after the sponsor first receives notice of the effect (§§ 812.46(b), 812.150(b)(1)).

For this device study, we will submit a report of a UADE to the manufacturer and the IRB as soon as possible, but no later than 10 working days after the investigators first learn of the event.

### **6.1.5 UP**

Any events that meet the criteria for “Unanticipated Problems” as defined by UNC’s IRB must be reported by the Study Coordinator using the IRB’s web-based reporting system.

Any unanticipated problem that occurs during the conduct of this study and that meets **at least** the first two criteria listed in section 8.2 must be reported to the UNC IRB using the IRB’s web-based reporting system.

## **6.2 Data and Safety Monitoring Plan**

The Principal Investigator will provide continuous monitoring of patient safety in this trial with periodic reporting to the Data and Safety Monitoring Committee (DSMC).

Meetings/teleconferences will be held at a frequency dependent on study accrual, and in consultation with the study Biostatistician. These meetings will include the investigators as well as protocol nurses, clinical research associates, regulatory associates, data managers, biostatisticians, and any other relevant personnel the principal investigators may deem appropriate. At these meetings, the research team will discuss all issues relevant to study progress, including enrollment, safety, regulatory, data collection, etc.

The team will produce summaries or minutes of these meetings. These summaries will be available for inspection when requested by any of the regulatory bodies charged with the safety of human subjects and the integrity of data including, but not limited to, the oversight (Office of Human Research Ethics (OHRE) Biomedical IRB, the Oncology Protocol Review Committee (PRC) or the North Carolina TraCS Institute Data and Safety Monitoring Board (DSMB).

The UNC LCCC Data and Safety Monitoring Committee (DSMC) will review the study on a regular (quarterly to annually) basis, with the frequency of review based on risk and complexity as determined by the UNC Protocol Review Committee. The UNC PI will be responsible for submitting the following information for review: 1) safety and accrual data including the number of study participants treated; 2) significant developments reported in the literature that may affect the safety of participants or the ethics of the study; 3) preliminary response data; and 4) summaries of team meetings that have occurred since the last report. Findings of the DSMC review will be disseminated by memo to the UNC PI, PRC, and the UNC IRB and DSMB.

## **7.0 STATISTICAL CONSIDERATIONS**

### **7.1 Study Design/Study Endpoints**

This is a nonrandomized, single-center, observational study. The purpose and endpoint of this study is to compare, in a radiologist reader study, the reader preference of the s-DCT scatter corrected images as compared to uncorrected s-DCT images.

Fifty (50) patients undergoing a clinical non-contrast CT for their lung nodules will be asked to have this procedure (scan) within 4 weeks of their clinical CT, with no intervening procedures or therapies involving the lung lesion (ie, excision or biopsy).

### **7.2 Sample Size and Accrual**

Assuming 50 cases are available for the comparison, and the standard deviation of the average reader score to be 2 (the range of the score is from +3 to -3), we will have at least 80% power to detect 0.7 confidence score of using scatter correction over without correction. In the data analysis, we will fit a linear mixed effect model with the confidence score as the outcome and a constant intercept. The working correlation matrix among readers is assumed to be compound symmetry. We will estimate grand mean from this model and test whether the mean confidence score is different from zero.

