## **1.0 BACKGROUND AND RATIONALE**

### **1.1 Study Synopsis**

This is a study that will evaluate the utility of a scatter reduction technique in reducing dose and increasing the sensitivity of stationary digital chest tomosynthesis (s-DCT) in the detection of lung lesions. Digital tomosynthesis is an imaging modality that produces 3D sectional information using x-ray projections acquired over a limited scanning angle. Scatter is known to be the primary source of image degradation in x-ray based imaging.

We have developed an approach that measures scatter through a low dose (3% of the conventional scan) scatter measurement technique. Preliminary studies have shown that scatter reduction in DCT can significantly improve quality. We plan to characterize the reader confidence in lung nodule detection in our scatter corrected chest tomosynthesis imaging approach as compared to our conventional chest tomosynthesis.

Fifty (50) patients who have undergone a clinical non-contrast CT with lung nodules will be asked to have an s-DCT (scan) within 4 weeks (+/- 2 week) of their clinical CT with no intervening procedures or therapies (i.e. biopsy of lung nodules). We will then perform a reader study to evaluate the radiologist reader confidence in images generated from the scatter reduction technique versus more conventional chest tomosynthesis imaging.

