## **4.0 STUDY PLAN**

### **4.1 STUDY SCHEMA**

This is a one arm study of 50 patients with one or more lung nodules who have had standard imaging (chest CT) who consent to undergo an experimental scatter correction s-DCT to characterize the number and extent of lung nodules. This experimental scan will be compared with CT to define the sensitivity of lung nodule detection among this group. The CT scan is used as the gold standard to assess for the presence of a nodule and will be interpreted by consensus to identify the target nodule for each case.

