### **7.4 Data Management**

The non-contrast chest CT, s-DCT, and SC s-DCT, if available, that are obtained of all eligible enrolled subjects will be de-identified for inclusion in the readers study. Copies of the clinical report forms as well as the de-identified images described in the preceding will be submitted for each case to the Study Coordinators for maintaining the study record and entering the data into a spreadsheet in preparation

for the reader study.

As an investigator initiated study, this trial will also be audited by the Lineberger Cancer Center audit committee every six or twelve months, depending on the participation of affiliate sites.

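### Section 7.2's power of at least 80% allows for no lost case and is narrowly missed even with all 50, while 50 also stands for patients asked and patients consenting

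*Combined protocol and SAP*

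**What the plan says.** The number 50 appears with three meanings.

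- **Asked.** Section 7.1: "Fifty (50) patients undergoing a clinical non-contrast CT for their lung nodules will be asked to have this procedure (scan". Section 1.1 is worded in nearly the same way.
- **Consenting.** Section 4.1 describes "50 patients with one or more lung nodules who have had standard imaging (chest CT) who consent to undergo an experimental scatter correction s-DCT".
- **Available for analysis.** Section 7.2 opens its power statement with "Assuming 50 cases are available for the comparison, and the standard deviation of the average reader score to be 2". The score runs from −3 to +3, and the section claims at least 80% power for a mean of 0.7.

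Section 7.4 lists the images that go into the reader study as "The non-contrast chest CT, s-DCT, and SC s-DCT, if available". No section gives a consent rate, a rate of unusable scans, an inflation of enrolment, a replacement rule, or a rule for a case with only one of the two tomosynthesis sets.

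The test is described in two ways. Section 7.2 asks whether the mean differs from zero. Section 7.3 asks whether it is larger than zero and sets the threshold at p < 0.05.

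**The concern.** The primary score compares corrected with uncorrected images of the same patient. A case therefore counts only if the patient consents, is scanned in the window without an intervening procedure, and has both sets reconstructed and read. The numbers asked, consenting and analysable are equal only if nothing is lost at any step.

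The protocol describes several points where a case could be lost. Patients are approached to see whether they are interested (Section 4.3.1). The scan needs a breath hold and comes with a separate correction scan (Section 4.3.2.1), and Section 1.4 says that patients with COPD or emphysema have difficulty holding their breath.

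A calculation with some margin could absorb a few losses. If it has none, a null result would be read against a power that the study did not have. It would also be unclear when accrual is complete: at 50 asked, 50 consented or 50 evaluable.

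**Working it through.** **Inputs**

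- Mean to detect δ = 0.7, SD of the average reader score = 2, n = 50 (Section 7.2).
- α = 0.05 (Section 7.3; Section 7.2 gives none).
- Sidedness: both readings are shown, because Sections 7.2 and 7.3 differ.
- Loss rate: none in the documents. I assume 10% and 20%, which leave 45 and 40 of 50 cases.

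**Method.** The model has only a grand mean and a random intercept per patient. If every reader scores every case, the test reduces to a one-sample test on the case averages. The normal approximation is

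power = Φ(δ√n / SD − z), with z = 1.645 one-sided or 1.960 two-sided.

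I also used the noncentral t with n − 1 degrees of freedom, which gives slightly lower figures.

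**Step 1: reproduce the plan's figure at 50 cases.**

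δ√n / SD = 0.7 × 7.071 / 2 = 2.475.

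- One-sided: Φ(2.475 − 1.645) = Φ(0.830) = 79.7%; by t, 78.7%.
- Two-sided: Φ(2.475 − 1.960) = Φ(0.515) = 69.7%; by t, 67.9%.

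The stated 80% is thus recovered only with a one-sided test and all 50 cases, and only by rounding.

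**Step 2: cases needed for 80%.** n = [SD × (z + 0.842) / δ]².

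- One-sided: (2 × 2.486 / 0.7)² = 50.5, so 51 cases (52 by t).
- Two-sided: (2 × 2.802 / 0.7)² = 64.1, so 65 cases (67 by t).

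**Step 3: power with fewer evaluable cases.**

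| Evaluable cases | One-sided, normal | One-sided, t | Two-sided, normal | Two-sided, t |
|---|---|---|---|---|
| 50 | 79.7% | 78.7% | 69.7% | 67.9% |
| 48 | 78.2% | 77.2% | 67.9% | 66.1% |
| 45 (10% loss) | 75.9% | 74.8% | 65.1% | 63.2% |
| 40 (20% loss) | 71.5% | 70.2% | 60.0% | 57.9% |

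By the one-sided normal figures, two lost cases cost about 1.5 points, a 10% loss about 4 points and a 20% loss about 8 points.

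**Step 4: mean detectable with 80% power.** SD × (z + 0.842) / √n.

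| Evaluable cases | One-sided, normal | One-sided, t | Two-sided, normal |
|---|---|---|---|
| 50 | 0.70 | 0.71 | 0.79 |
| 45 | 0.74 | 0.75 | 0.84 |
| 40 | 0.79 | 0.80 | 0.89 |

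**The case against.** The strongest reply is that Section 7.2 states its condition openly: the power is for 50 available cases, if they are available. Section 4.1 gives the design as 50 consenting patients, and the talk of asking 50 patients is most naturally loose wording for the same group. Exposure to loss is limited. Consent may be taken on arrival for the scan, there is a single research visit, and planned intervening procedures are an exclusion. One or two lost cases would hardly matter.

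The SD of 2 may also be cautious. A single score spread evenly over the seven points has variance (7² − 1)/12 = 4, so SD 2, and an average over three readers would usually vary less. At an illustrative SD of 1.8, one-sided power by t is 82% at 45 cases and 78% at 40. Section 1.5 calls the work a pilot.

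Much of this stands, and it rules out three stronger readings.

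- A reader might infer that Section 7.4 expects corrected sets to be missing. The words permit absence without predicting it, and the condition may apply to the whole list of images.
- A reader might take 50 as a cap on invitations and work out the power after refusals. Section 4.1 counts consenting patients, Section 4.3.1 sets no cap on approaches, and no consent rate is given.
- A reader might conclude that accrual will fail to yield 50 cases. Nothing in the documents shows that.

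The reply does not rescue the stated figure. On the plan's own SD, at least 80% is not reached at 50 cases under either sidedness. The plan gives no pilot SD that would justify a smaller value. A stated assumption of 50 available cases still needs an enrolment count that is defined separately from it.

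**Conclusion.** The point holds in a limited form. One number serves for patients asked, patients consenting and cases analysed, with no allowance for loss, in a calculation that has no margin.

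It would be wrong to infer that the claim is met so long as nobody is lost. With all 50 cases the one-sided power falls just short, by 0.3 to 1.3 points. Under Section 7.2's own two-sided wording the shortfall is 10 to 12 points, which is more than a 20% loss costs under the one-sided test. Sidedness is therefore the larger influence on the figure and has to be settled before any power is restated.

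The effect of losses is moderate: small for one or two cases, and about 4 and 8 points for losses of 10% and 20%. These sizes rest on SD 2, a mean of 0.7, α = 0.05 and loss rates that are my assumptions. A smaller true SD would offset them.

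**What to change.** 1. In Sections 1.1, 4.1 and 7.1, count 50 in one way, as patients enrolled and scanned.
2. In Section 7.2, define the power denominator as evaluable cases (both image sets obtained and read), and state the loss assumed between enrolment and evaluation.
3. Use one sidedness in Sections 7.2 and 7.3, and replace the claim of at least 80% with the power for the expected number of evaluable cases under that test. For example, if 45 of 50 are taken to be evaluable and the test is one-sided at 5%, power is about 75% for a mean of 0.7, or 80% for a mean of 0.75. The 45 is illustrative; the study team should put in its own expected loss.
4. In Section 7.4, say what happens to a case whose corrected set is unavailable.

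The cost is wording in these sections and a less favourable stated power. No extra patients are needed.

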### **7.3 Data Analysis Plans**

The study will be performed as a reader confidence study. For each comparison, the average confidence scores and the corresponding standard deviations will be reported. Furthermore, to test whether the mean confidence score is larger than zero, a linear mixed effect will be used to analyze data, where the outcome variable is the confidence scores collected in this study and only a grand mean parameter is in the independent list. Additionally, a random intercept is used in the model to account for the correlation among readers when reading the images from the same patient. The Wald's test based on model fit will be used to test whether the grand mean parameter is larger zero. When the p-value from this test is less than 0.05, it will be concluded that there exists significant evidence that readers have more confidence with the s-DCT scatter corrected modality compared to the conventional s-DCT.

The reader preference study form (including both primary and secondary evaluations) is located in the Appendix.

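### Sections 7.2 and 7.3 disagree on whether the primary test is two-sided or one-sided, and the claimed 80% power fits only the one-sided version, and then only to rounding

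*Combined protocol and SAP*

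**What the plan says.** Section 7.2 sets out the sample size reasoning. It starts from "Assuming 50 cases are available for the comparison", takes "the standard deviation of the average reader score to be 2" on a scale from -3 to +3, and concludes that "we will have at least 80% power to detect 0.7 confidence score of using scatter correction over without correction". It gives no significance level. It then describes the analysis: a linear mixed model with only an intercept, whose grand mean is used to "test whether the mean confidence score is different from zero".

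Section 7.3 describes the same intercept-only mixed model and the same grand mean. Its stated aim is "to test whether the mean confidence score is larger than zero", and the Wald "test based on model fit will be used to test whether the grand mean parameter is larger zero". The decision rule follows: "When the p-value from this test is less than 0.05, it will be concluded that there exists significant evidence" that readers are more confident with the scatter-corrected images.

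Neither section uses the term one-sided or two-sided, and nothing in the document says which section takes precedence.

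**The concern.** This is the only formal test of the primary endpoint, and the document defines it in two incompatible ways. A result whose one-sided p-value lies between 0.025 and 0.05 would be positive under section 7.3 and negative under section 7.2 read at a two-sided 0.05. If the choice is left until the data are seen, the result can decide the test.

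The power statement is affected too. It appears in the section with the two-sided wording, but its figure appears to come from a one-sided calculation. A reader who takes 7.2 at its word would believe the chance of missing a true mean of 0.7 is at most 20%, when for the test worded there it is 30–32%.

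**Working it through.** **Inputs.** From section 7.2: n = 50 cases, standard deviation 2 for the per-case score averaged over readers, effect 0.7, null value 0. From section 7.3: significance level 0.05, not labelled one- or two-sided. Applying that 0.05 to the two-sided wording of 7.2 is an assumption, because 7.2 gives no level.

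**Common quantities.** With one averaged score per case, this is a one-sample test of a mean.

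- Standard error = 2/√50 = 0.2828
- Standardised effect = 0.7/0.2828 = 2.475

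**Reproducing the plan's figure (one-sided 0.05).**

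- Normal: Φ(2.475 − 1.645) = Φ(0.830) = 79.7%
- Noncentral t, 49 df: 78.7%

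This matches the stated 80% to rounding. Strictly, it falls short of *at least* 80%, which would need 51 cases (normal) or 52 (t).

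**The test as worded in 7.2 (two-sided 0.05).**

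- Normal: Φ(2.475 − 1.960) = Φ(0.515) = 69.7%
- Noncentral t, 49 df: 67.9%

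**Comparison of the two versions** (normal / t):

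| | One-sided 0.05 (7.3) | Two-sided 0.05 (7.2 wording) |
|---|---|---|
| Power at a mean of 0.7 | 79.7% / 78.7% | 69.7% / 67.9% |
| Chance of missing a mean of 0.7 | 20.3% / 21.3% | 30.3% / 32.1% |
| Mean detectable with 80% power | 0.703 / 0.713 | 0.792 / 0.808 |
| Cases needed for 80% power at 0.7 | 51 / 52 | 65 / 67 |
| Smallest significant observed mean (SD 2) | 0.465 / 0.474 | 0.554 / 0.568 |

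The last row is critical value × 0.2828, with critical values 1.645 / 1.677 one-sided and 1.960 / 2.010 two-sided.

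**Conflicting verdicts.** An observed mean between the two thresholds in the last row is positive under 7.3 and negative under 7.2. At a true mean of 0.7, the probability of landing there is the difference in power: 0.797 − 0.697 = 0.100 (normal), or 0.7869 − 0.6795 = 0.107 (t).

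**Sensitivity to the meaning of the standard deviation.** Suppose 2 were the standard deviation of a single reader's score. With three readers and common correlation ρ, the average would have standard deviation 2√((1 + 2ρ)/3). Two-sided power would then be 85.8% (normal) or 84.4% (t) at ρ = 0.5, 80.7% or 79.1% at ρ = 0.65, and 79.0% (normal) at ρ = 0.7. The document gives no value for ρ.

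**The case against.** The best defence is that section 7.3 is the analysis plan proper. It holds the only significance level, the only named test and the only decision rule, and that rule is directional. The power sentence in 7.2 is directional as well, since it speaks of detecting a benefit "to detect 0.7 confidence score of using scatter correction over without correction". On this view the calculation was made for a one-sided 0.05 test, it reproduces within 0.3 points by the normal approximation, and one sentence in 7.2 is loosely worded. That may well be how the figure arose. But 7.2 also describes the analysis to be carried out, no text subordinates it to 7.3, and a Wald test can be run either way. Even if 7.3 governs, 7.2 has to be corrected.

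A second objection concerns the standard deviation. A score spread evenly over the seven categories from -3 to +3 has variance 28/7 = 4, so a standard deviation of exactly 2, which suggests the figure may describe a single reader. An average over three readers with that spread would keep a standard deviation of 2 only if they agreed perfectly. Under the single-reader reading, two-sided power could reach 80%, depending on the correlation. The re-reading in reverse order under section 4.3.3 might also add scores per case. However, 7.2 attaches the 2 to the average reader score and offers no correlation from which to take credit for averaging. This objection bears on the power figure only; the conflict over sidedness is untouched.

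It is also fair to say that this is a single-centre pilot whose images do not guide care, and that the choice between normal and t reference moves the power by only 1 to 2 points.

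**Conclusion.** The concern holds. The primary test is two-sided as worded in 7.2 and one-sided as worded in 7.3, and the difference can change the trial's conclusion. The claim of at least 80% power is met only to rounding under the one-sided test (78.7–79.7%) and is missed by about 10 to 12 points under the two-sided test (67.9–69.7%).

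The power figures rest on 50 evaluable cases, on reading 2 as the standard deviation of the per-case average as 7.2 states, and, for the two-sided case, on borrowing the 0.05 from 7.3. The 10–11% chance of conflicting verdicts applies at a true mean of 0.7 with a standard deviation of 2. The contradiction itself depends on none of these assumptions. It should be settled before the readings are analysed, because a choice made afterwards would not be credible.

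**What to change.** Keep 50 patients. Before the readings are analysed, state one sidedness and one significance level in identical terms in 7.2 and 7.3, and restate the power accordingly. Either choice is workable:

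- **Two-sided 0.05.** In 7.3, replace both statements that the mean is tested as larger than zero with a test of a difference from zero, and conclude in favour of scatter correction only if the estimate is also positive. In 7.2, state about 68% power for a mean of 0.7 and 80% power for a mean of 0.81 (about 70% and 0.79 if the Wald statistic is referred to the normal distribution).
- **One-sided 0.05.** In 7.2, reword the test as whether the mean exceeds zero, and replace the claim of at least 80% power with about 79% (about 80% on the normal reference).

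In both cases, say which reference distribution is used. If the 2 was meant as a single-reader standard deviation, say so and give the assumed correlation among readers.

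The cost is a few sentences in two sections, with no added patients and no change to data collection. The two-sided choice raises the observed mean needed for a positive result from about 0.47 to 0.55–0.57 and leaves a less favourable power statement. The one-sided choice means a result favouring the uncorrected images cannot be declared significant.
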